5.1 Overall Study Design

This is a Phase 2, multicenter, randomized, double-blind, placebo-controlled, parallel-group study in patients with DPNP.

Scheduled study visits in the clinic will occur during Screening; at the initiation of the 2-week single-blind placebo Run-in Period; on Day 1 (Baseline) and during Weeks 2, 4, and 6 of the double-blind Treatment Period, and at Week 11 (Week 5 of the single-blind Safety Follow-up Period).

[figure not shown]
Male and female patients of nonchildbearing potential, age 18 years and above, diagnosed with T1DM or T2DM and with chronic DPNP, and who meet all inclusion and no exclusion criteria are eligible for enrollment.

Eligible patients may continue use of medications prescribed for DPNP including pregabalin, gabapentin, and antidepressant medications, as long as they have been at stable doses for at least 1 month prior to Screening and are willing to maintain their doses for the duration of the study. Use of any opioid medications for the management of DPNP within the 2 months prior to Screening is not permitted.

The treatment schema is summarized in Figure 5.1-1.

Figure 5.1–1 Treatment Schema

R = randomization EOT = end of treatment EW = early withdrawal

- ** Maintenance Dose (Day 2 Week 11 Visit)
- @ Day 1 may occur up to 2 weeks plus 3 days after start of the Run-In period

2 Optional Substudies:

- PK Evaluation and possible biomarker analysis (up to 30 patients) —
 Days 1 and 2, Week 2, Week 4, Week 6 or EOT/EW, Week 11 or 35 Days after
 EOT/EW
- Exit Phone Interview Within 2 to 3 weeks following the Week 6 Visit or EOT/EW

^{*-} Loading Dose (Day 1)

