6.6 Method of Assigning Patients to Treatment

Patients will be randomly assigned among 3 parallel treatment groups in a 1:1:1 manner. A randomization schedule will be centralized and stratified by the ADPS during the Run-in period based on moderate or severe pain. The randomization schedule will also account for the optional PK and biomarkers substudy. The desired balances will be accomplished by use of randomly permuted blocks of fixed size. An Interactive Voice/Web Response System (IXRS) will be used as a central mechanism to assign patients to study treatment.

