2.2 Overall Study Design

This is a Phase 2, multicenter, randomized, double-blind, placebo-controlled, parallel-group study in patients with DPNP. Up to 282 patients are expected to enroll in this study.

Scheduled study visits in the clinic will occur during Screening; at the initiation of the 2-week single-blind placebo Run-in Period; on Day 1 (Baseline) and during Weeks 2, 4, and 6 of the double-blind Treatment Period, and Week 11 of the single-blind Safety Follow-up Period.

Male and female patients of age 18 years and above, diagnosed with T1DM or T2DM and with chronic DPNP, and who meet all inclusion and no exclusion criteria are eligible for enrollment.

Eligible patients may continue use of 1 medication prescribed for DPNP including pregabalin, gabapentin, and antidepressant medications, as long as they have been at stable doses for at least 1 month prior to screening and are willing to maintain their doses for the duration of the study. Use of any opioid medications for the management of DPNP within the 2 months prior to Screening is not permitted.

Screening Period: After signing the Informed Consent Form (ICF), all patients will enter a Screening Period of up to 2 weeks. Following confirmation of eligibility criteria, patients will enter the following study periods:

Run-in Period: After meeting Screening eligibility criteria, patients will enter a 2-week single-blind Run-in Period. On Day 1 of the Run-in period, patients will be administered 4 tablets of single blind study drug at the site. For the remainder of the Run-in Period, patients will take a single tablet of study drug in the morning. Each evening patients will rate and record the intensity of their DPNP over the previous 24 hours based on Question 5 of the BPI-DPN by answering the question "Please rate your pain due to your diabetes by indicating the one number that best describes your pain on the average." (0 [no pain] to 10 [pain as bad as you can imagine]) in their daily pain diary and will rate the interference of pain with sleep by completing Question 9F of the BPI-DPN. The ADPS will be calculated using all available daily pain diary data. In order to qualify for randomization, patients must

CONFIDENTIAL

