7.4 Demographics and Other Baseline Characteristics

Demographic and baseline characteristics will be listed and summarized by treatment group and overall for the mITT population. Standard descriptive statistics will be presented for the continuous variables of:

- Age at time of Informed Consent (years)
- Weight (kg), to convert pounds (lbs) to kilograms, multiply the pound value by 0.45359237
- Height (cm), to convert inches (in) to centimeters, multiply the inches value by 2.54

Statistical Analysis Plan Final v3.0

Lexicon Pharmaceuticals, Inc.
Protocol ID: LX9211.1.201-DPN

Labcorp Study ID: 000000198624

- Body mass index (BMI) (kg/m²)
- Sitting systolic blood pressure (BP) (mm Hg)
- Sitting diastolic BP (mm Hg)
- Pulse rate (beats per minute [bpm])
- Respiration rate (breaths/min)
- Temperature (C), to convert Fahrenheit (F) to Celsius, (Fahrenheit value (F) – 32) * 5/9
- HADS-Depression and HADS-Anxiety subscores

The total counts and percentages of patients will be presented for the categorical variables of:

- Age at time of Informed Consent (grouped as <75 years, ≥ 75 years)
- Sex
- Race
- Ethnicity
- Fertility status (females only)
- Method of contraception
- Baseline pain severity categorized by randomization strata (as derived using average pain scores collected during the 14-day Run in data)
- Baseline ADPS (as derived using week 2 of Run-in data)
- DPNP drug use (Yes, No)

A summary of Baseline physical examination data will be presented by treatment group and overall for the mITT population.

Other baseline measurements, such as laboratory evaluations and ECG, will be summarized by treatment group with the post-Baseline measurements.

No formal tests of statistical significance will be performed on the demographic and Baseline characteristics data.

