7.6.1 Primary Efficacy Analysis

The primary endpoint is the change from Baseline to Week 6 in ADPS, based on Question 5 of the BPI-DPN, the 11-point scale (0 [no pain] to 10 [pain as bad as you can imagine]). The primary analysis will be based on observed data including data measured after the initiation of rescue medications.

Baseline is defined as the average of the Week 2 Run-in Period data collected by patients in the daily pain diary, provided that ≥ 5 days from that period are available for analysis. The post-Baseline values will be calculated by week as the mean value of the Question 5 for ADPS of the BPI-DPN, rated by patients each evening and collected during the target week period. A minimum of 4 non-missing data within the target week period is required for the calculation. The change from

Baseline values at post-Baseline weeks will be calculated as the absolute difference between the Baseline value and post-Baseline values, ie

$$\text{change from Baseline} = \text{post-Baseline value} - \text{Baseline value}$$

The ADPS calculated for each post-Baseline week until Week 6, and the change from Baseline in ADPS at post-Baseline weeks until Week 6 will be summarized by Week using standard descriptive statistics. Data from all study visits, scheduled and unscheduled, and from the daily pain diary will be listed.

A restricted maximum likelihood-based, MMRM approach will be used to assess the difference between LX9211 and placebo in the primary endpoint (ie, change from Baseline to Week 6 in the ADPS derived from data collected daily from Question 5 of the BPI-DPN instrument). The MMRM model will include fixed effects of treatment, week, treatment-by-week interaction, the randomization stratum of Baseline pain severity (moderate, severe), and Baseline ADPS score as a covariate. An unstructured covariance structure will be used to model the within-patient error. Other covariance structures will be explored should convergence not be met. The Kenward-Roger approximation will be used to estimate the denominator degrees of freedom.

The adjusted mean change in ADPS from baseline to Week 6 for each treatment group and the 95% confidence intervals (CIs) will be estimated in the framework of this model, as well as the between-group differences (comparing each LX9211 treatment group to placebo) and the 95% CIs for the difference.

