7.6.3 Sensitivity Analysis

In the event that rescue medication is used, a supplementary MMRM model will be applied to the primary endpoint dataset that excludes data collected after the initiation of the rescue medication using the mITT population. This model will be parameterized in the same manner as will be used for the primary analysis of this endpoint.

In addition, to assess the robustness of the MMRM analyses performed under the MAR assumption, and given the long half-life of LX9211, PMMs with copy reference-based imputation methods will be applied on both datasets (with and without data collected after the initiation of the rescue medication) using the mITT population.

CONFIDENTIAL

Document Date: 07JUN2022

Page 32 of 55

ST-AD-008 version 05

Methods will be adopted to estimate for both non-monotone and monotone missing data patterns. Imputations for the non-monotone missing data pattern will be the initial step. The imputation algorithm based on Monte Carlo Markov Chain methodology will be used assuming a MAR mechanism for the missing data; 100 imputations will be used. Then multiple imputations will be performed to assign the response variable at consecutive study weeks in a sequential manner for the monotone missing data pattern. For this chain-based method, control-based imputation will be applied so that there is no direct use of observed data from the LX9211 treatment groups in estimating the imputation model. The method is derived such that it builds its imputation only on the placebo group data. The imputed datasets will be combined by use of Rubin's rule and analyzed using an analysis of covariance (ANCOVA) model fitted for the fixed effects of treatment, the randomization stratum of the Baseline pain severity (moderate, severe), and the continuous fixed covariate of Baseline score. The ANCOVA analysis will be performed at Week 6 only. Summary statistics from applying the ANCOVA model across the multiple imputed datasets will be combined to obtain an overall estimate of the treatment group differences.

Sensitivity analyses are not planned for analyses of the secondary or other efficacy endpoints.

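### Background DPNP treatment is allowed and recorded but is not adjusted for in the primary model; adding it is a cheap, small improvement, not the repair of a validity error.

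*SAP*

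**What the plan says.** Protocol 5.1 states: "Eligible patients may continue use of medications prescribed for DPNP including pregabalin, gabapentin, and antidepressant medications". Doses must have been stable for at least a month before Screening and are to be held for the whole study. SAP 2.2 words the permission differently: "Eligible patients may continue use of 1 medication prescribed for DPNP including pregabalin, gabapentin, and antidepressant medications". The two texts disagree on how many such drugs a patient may keep and must be reconciled.

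Background treatment is not a randomisation factor. Protocol 6.6 says: "A randomization schedule will be centralized and stratified by the ADPS during the Run-in period based on moderate or severe pain". It adds: "The randomization schedule will also account for the optional PK and biomarkers substudy".

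The primary MMRM (Protocol 10.4.2.1, SAP 7.6.1) has treatment, week, their interaction, and "the randomization stratum of Baseline pain severity (moderate, severe), and Baseline ADPS score as a covariate". The copy-reference ANCOVA in SAP 7.6.3 has treatment, "the randomization stratum of the Baseline pain severity (moderate, severe), and the continuous fixed covariate of Baseline score". Neither has a term for background treatment.

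The SAP does use the factor elsewhere. DPNP drug use, yes or no, is a baseline characteristic in SAP 7.4 and a subgroup factor for the primary endpoint in SAP 7.6.4. The subgroup is defined by named drugs among concomitant medications, and the subgroup models keep the primary covariates.

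**The concern.** Two patients with the same Baseline ADPS may not be alike. One may still have that pain despite a stable analgesic, while the other is untreated. If such patients change differently over six weeks, background treatment is prognostic given Baseline, and two things follow.

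- If one arm happens to contain more users than placebo, the observed Week 6 difference moves by the imbalance times the residual effect, and the planned model does not take that out.
- Even with balanced arms, the variation due to background treatment stays in the error term.

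The two doses share one placebo arm, so an unusual placebo arm would move both contrasts in the same direction. If the baseline table then showed an imbalance, any adjustment would be post hoc and open to dispute. The subgroup results would not settle it, because they give separate estimates for users and non-users and not one adjusted overall difference.

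**Working it through.** **The plan's own figure.** Protocol 10.1 gives 75 completers per arm, a difference of 1 unit, SD 2, two-sided Dunnett α = 0.05, 80% power and 20% dropout. Protocol 10.4.5.7 gives a per-comparison one-sided level of 0.0141, that is 0.0282 two-sided.

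- n per arm = 2 × SD² × (z for 0.0141 + z for 80% power)² / δ² = 2 × 4 × (2.194 + 0.842)² / 1 = 73.7, so 74.
- With 75 per arm, SE = 2 × √(2/75) = 0.327 and power is 80.7%.
- An exact Dunnett calculation (222 df, critical value 2.226) gives 79.8% for one comparison, and 80.7% for at least one when only one dose is active.
- 75 / 0.8 = 93.75, so 94 per arm and 3 × 94 = 282.

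The stated sample size reproduces.

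**Assumptions for the effect of adjustment.** The documents give neither the proportion on background treatment (p) nor its effect on ADPS change given Baseline ADPS (g). I take p = 0.20-0.50 and g = 0.25-1.0 point, with 75 per arm and a variance of 4 that includes this component.

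- 95% limit of the between-arm imbalance = 1.96 × √(2p(1-p)/75)
- Shift of the contrast at that limit = limit × g
- Residual SD after adjustment = √(4 - p(1-p)g²)

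| p | g | 95% limit (percentage points) | Shift (points) | Residual SD | Power | n per arm |
|---|---|---|---|---|---|---|
| 0.20 | 0.25 | ±12.8 | ±0.032 | 1.997 | 80.8% | 74 |
| 0.20 | 1.0 | ±12.8 | ±0.128 | 1.960 | 82.4% | 71 |
| 0.35 | 0.5 | ±15.3 | ±0.076 | 1.986 | 81.3% | 73 |
| 0.50 | 0.25 | ±16.0 | ±0.040 | 1.996 | 80.9% | 74 |
| 0.50 | 1.0 | ±16.0 | ±0.160 | 1.936 | 83.3% | 70 |

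With all 94 per arm the limits shrink by √(75/94) = 0.89, so the largest shift is about 0.14. A typical imbalance of one SD (6.5 to 8.2 percentage points) moves the contrast by 0.016 (0.065 × 0.25) to 0.082 (0.082 × 1.0), against the SE of 0.327.

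**Error rates.** A simulation of 40,000 two-arm trials with no treatment effect used the extreme corner (p = 0.5, g = 1.0, 75 per arm, one comparison at a nominal two-sided 5%).

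- Overall type I error was 5.2% with or without the covariate, and both estimators were unbiased.
- The SD of the estimate was 0.328 unadjusted and 0.318 adjusted.
- In the 5% of trials with an imbalance of 16 points or more, the mean shift was 0.20 points. This exceeds 0.16 because it averages over trials at and beyond the limit. The rejection rate in those trials was 8.3% unadjusted and 4.6% adjusted.

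**The case against.** The case against is strong on validity. Randomisation balances background use in expectation, the planned standard error already carries the chance variation, and every unadjusted prognostic factor passes into a contrast in this way. Because doses are stable before Screening and held afterwards, Baseline ADPS and the severity stratum are both measured on background treatment and take up part of its effect. A residual effect of 1.0 point would equal the whole targeted drug effect, so the upper end of the range is generous. All of this stands.

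It can also be said that SAP 7.6.4 already reruns the MMRM within users and non-users, where imbalance in this yes/no factor cannot operate, and that SAP 7.4 would show an imbalance. Both are true, and both would help to reveal a problem. But the subgroup analyses are exploratory and yield no single adjusted contrast.

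Finally, the change is more than a line in the SAP. Protocol 10.4.2.1 fixes the same covariates, and the trial has a planned unblinded interim analysis of the primary endpoint (Protocol 10.4.5.7, SAP 7.8). Changing the primary model after that look invites an objection of its own. This stands and shapes the fix.

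**Conclusion.** Leaving background treatment out of the model is a missed low-cost improvement. A reader might infer that the primary estimate is biased, that the type I error is inflated, or that randomisation without this stratum is defective. The documents do not support any of these: allocation is random, the overall error rate is unaffected, and the 8.3% figure applies only to the few trials with the largest imbalance under the most extreme assumptions.

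What remains is a conditional shift of at most 0.03-0.16 points in 95% of cases, and a power gain of about 0 to 3 percentage points (80.7% to 80.8-83.3%). Both rest on assumed values of p and g. If background treatment has no residual effect given Baseline ADPS, adjustment gains nothing and costs almost nothing.

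**What to change.** Before unblinding:

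- Define DPNP drug use (yes/no) from the SAP 7.6.4 drug list as ongoing on Day 1. Exclude drugs started after the first dose. SAP 7.4.2 counts medications that start on or after the first dose as concomitant, so the existing subgroup definition could let in a post-randomisation variable.
- Add this factor and its interaction with week as fixed effects in the primary MMRM. A main effect alone would assume the same difference at every week, while the contrast of interest is at Week 6.
- Add the factor as a fixed effect in the Week 6 copy-reference ANCOVA.
- Record the change in SAP Section 8 as a departure from the model in Protocol 10.4.2.1.

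If the primary model is to stay unchanged after the unblinded interim, prespecify the same model as a sensitivity MMRM.

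Cost: one parameter in the ANCOVA, and one plus five for the week interaction in the MMRM (Weeks 1 to 6); a derivation from medication records that the eCRF already holds; and a documented change from the protocol model.

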7.6.2 Secondary Efficacy Analysis

Analysis of the secondary efficacy endpoints will be based on the mITT population. Descriptive statistics for all the secondary efficacy endpoints will be presented by treatment group and by study visit/week where appropriate. Data from all study

visits, scheduled and unscheduled, and from the daily pain diary will be listed. Post-Baseline data through Week 6 will be used in the analyses where inferential statistics are presented, including observations occurring after discontinuation of study drug. Figures displaying mean change from Baseline, LS mean change at Week 6, and bar charts displaying proportions, will be presented by treatment group.

Continuous secondary efficacy endpoints: BPI-DPN scores, measured at multiple time points, will be analyzed using a similar modeling strategy as for the primary endpoint.

The ordinal secondary endpoint, PGIC response at Week 6, will be analyzed using an analysis of variance (ANOVA) model to test and estimate the treatment effect.

Categorical secondary endpoints: the proportion of responders based on Question 5 of BPI-DPN and the proportion of patients discontinuing study treatment due to lack of efficacy will be compared between treatments using a Cochran-Mantel-Haenszel (CMH) test stratified by the randomization factor of Baseline pain severity (moderate, severe). Patients with missing measurement at Week 6 will be considered non-responders. In general, a non-responder imputation (NRI) rule will be applied to assign outcomes to all study weeks with missing observations.

The Kaplan-Meier (KM) method will be used to generate statistical summaries of the time to loss of efficacy variable among patients who achieve $\geq 30\%$ reduction in ADPS based on Question 5 of the BPI-DPN from Week 6 to Week 11.

The qualitative patient interview substudy will be managed by a separate vendor (RTI-Health Solutions, Research Triangle Park, NC). The data analysis methods they employ will be detailed in a separate statistical analysis plan and the results will be reported separately by them.

7.6.2.1 Proportion of patients with $\geq 30\%$ reduction in pain intensity in ADPS based on Question 5 of the BPI-DPN from Baseline to Week 6

Baseline and Week 6 ADPS scores will be based on the same mean values as derived for the primary endpoint. The frequency and percentage of patients with $\geq 30\%$ reduction in pain intensity from Baseline at Week 6 will be presented by treatment group. Response/Non-response categories will be defined as:

- If % change from Baseline $\leq (-30)$ \rightarrow Response
- If missing % change from Baseline or $> (-30)$ \rightarrow Non-response

Where % change from Baseline = $100 * (\text{post-Baseline value} - \text{Baseline value}) / \text{Baseline value}$.

This endpoint will use a CMH test stratified by the different levels of the randomization stratification factors of Baseline severity score (moderate, severe). The treatment group comparisons of each dose level of LX9211 (100 mg/10 mg or 200 mg/20 mg) versus placebo will be performed at Week 6 only, with descriptive statistics provided for each week. 95% CIs for the difference between 2 proportions will be calculated using the asymptotic Wald method.

7.6.2.2 Proportion of patients with $\geq 50\%$ reduction in pain intensity in ADPS based on Question 5 of the BPI-DPN from Baseline to Week 6

Baseline and Week 6 ADPS scores will be based on the same mean values as derived for the primary endpoint. The frequency and percentage of patients with $\geq 50\%$ reduction in pain intensity from Baseline at Week 6 will be presented by treatment group. Response/Non-response categories will be defined as:

- If % change from Baseline $\leq (-50)$ \rightarrow Response
- If missing % change from Baseline or $> (-50)$ \rightarrow Non-response

Similarly, this endpoint will be analyzed as for [Section 7.6.2.1](#).

7.6.2.3 Change from Baseline to Week 6 in pain severity and pain interference based on questions from the BPI-DPN

The following pain severity and pain interference categories, completed at the time of the clinic visit (unless noted otherwise), will be analyzed separately:

- Pain at its worst
- Pain at its least
- Pain right now
- Interference score averaged over Questions 9A-G
- General activity
- Mood
- Walking ability
- Normal work
- Relations with other people
- Sleep
- Enjoyment of life

The interference score, averaged over Questions 9A-G, will be calculated as the mean of the 7 interference categories collected in Questions 9A-G during the clinical visits as long as at least 50% (ie, at least 4 of 7) of the scores are non-missing.

The change from Baseline to Week 6 in pain severity and pain interference will be summarized using standard descriptive statistics and the treatment effect will be evaluated using a similar MMRM method as specified for the primary efficacy analysis of change from Baseline to Week 6 in ADPS where the time point will be

CONFIDENTIAL

substituted by Visit instead of Week. The Baseline covariate included in the model is the Baseline value of the dependent variable under analysis.

In addition, the change from Baseline to Week 6 in pain interference with sleep based on Question 9F, rated by patients and collected each evening in the daily pain diary will be summarized using standard descriptive statistics and the treatment effect will be evaluated using a similar MMRM method as specified for the primary efficacy analysis of change from Baseline to Week 6 in ADPS. In this case, the Baseline value for the interference with sleep using Question 9F of the BPI-DPN is defined as the value collected at the time of the clinic visit on Day 1. The post-Baseline values will be calculated by week as the mean value of the Question 9F of the BPI-DPN, rated by patients each evening and collected during the acceptable week period. A minimum of 4 non-missing data within the target week period is required for the calculation.

7.6.2.4 Proportion of patients discontinuing treatment due to lack of efficacy based on data collected for Question 5 of the BPI-DPN

This endpoint will be derived as follows:

1. Condition on the eCRF item if the patient stopped study treatment with reason of Lack of Efficacy.
2. If "Yes" to the above, calculate the % change from Baseline of ADPS based on Question 5 of the BPI-DPN during the double-blind Treatment Period, starting at Baseline and ending on the last assessment before the patient stopped study treatment. No minimum number of assessments is required.
3. If the derived value in #2 $\geq 30\%$, then the patient is classified as a "responder". If otherwise (including all mITT patients), then the patient is classified as a "non-responder".

Where % change from Baseline = $100 * (\text{last week of treatment value} - \text{Baseline value}) / \text{Baseline value}$.

The frequency and percentage of patients discontinuing treatment during the double-blind Treatment Period due to lack of efficacy will be presented by treatment group. Similarly, this endpoint will be analyzed as described in for [Section 7.6.2.1](#).

7.6.2.5 Patient Global Impression of Change (PGIC) at Week 6

The PGIC, a 7-point rating scale, will assess the patient's belief about their overall improvement experienced at the end of treatment.

The frequency and percentages of patients within each category at Week 6 will be presented by treatment group. The treatment effect will be evaluated using an

ANOVA model with treatment and randomization stratum of Baseline pain severity (moderate, severe) as independent variables. Least-square means of PGIC in each treatment group and the difference between LX9211 and placebo for each comparison, along with their 95% CIs and p-value will be presented.

7.6.2.6 Time to loss of efficacy from Week 6 to Week 11 among patients achieving $\geq 30\%$ reduction in pain intensity in ADPS based on Question 5 of the BPI-DPN at Week 6

Time to loss of efficacy is defined as the time from the date of Week 6 visit to the date of termination of safety follow-up due to lack of efficacy. Termination of safety follow-up due to other reasons and death are competing risk. Patients who have terminated the safety follow-up due to any reason other than lack of efficacy after Week 6 visit or have completed the study through Week 11 will be censored at the date of the last ADPS assessment based on Question 5 of the BPI-DPN collected by patients in the daily pain dairy.

Time to loss of efficacy (weeks) = (date of termination of safety follow-up due to lack of efficacy or censoring – date of Week 6 visit + 1) / 7.

Only patients who achieved $\geq 30\%$ reduction in pain intensity in ADPS based on Question 5 of the BPI-DPN from Baseline to Week 6 will be included in the analysis of time to loss of efficacy.

Kaplan-Meier estimates and the associated 95% CIs of the median, 25th, and 75th percentile will be presented. The 2-sided 95% CIs will be computed using the log-log transformation.

The minimum and maximum time to loss of efficacy (using censored and event times) will also be presented.

The survivor function will be displayed graphically by treatment group using a KM curve.

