3.2 Secondary Efficacy Endpoints

The secondary efficacy endpoints are to be assessed in each LX9211 dose group versus placebo comparison for each of the following variables listed below:

- Proportion of patients with $\geq 30\%$ reduction in pain intensity in ADPS based on Question 5 of the Brief Pain Inventory - DPN (BPI-DPN) from Baseline to Week 6
- Proportion of patients with $\geq 50\%$ reduction in pain intensity in ADPS based on Question 5 of the Brief Pain Inventory - DPN (BPI-DPN) from Baseline to Week 6
- Change from Baseline to Week 6 in the severity of pain and interference of pain with sleep and other aspects of the patient's life based on the Brief Pain Inventory (BPI) Short Form for diabetic peripheral neuropathy (BPI-DPN) including the following:
 - Pain at its worst
 - Pain at its least
 - Pain right now
 - Interference score averaged over Questions 9A-G
 - General activity
 - Mood
 - Walking ability
 - Normal work
 - Relations with other people
 - Sleep
 - Enjoyment of life
- Proportion of patients discontinuing treatment due to lack of efficacy defined as increase in ADPS based on Question 5 of the Brief Pain Inventory - DPN (BPI-DPN) from Baseline of 30%
- Patient Global Impression of Change (PGIC) at Week 6
- Time to loss of efficacy from Week 6 to Week 11 among patients achieving at least 30% reduction in pain intensity in ADPS based on Question 5 of the Brief Pain Inventory - DPN (BPI-DPN) at Week 6

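### Lack-of-efficacy discontinuation, probably a sparse endpoint, is given a Wald interval with no sparse-data fallback

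*SAP*

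**What the plan says.** For the ≥30% responder endpoint, SAP 7.6.2.1 says: "This endpoint will use a CMH test stratified by the different levels of the randomization stratification factors", namely baseline pain severity (moderate, severe). For the interval it says only that "95% CIs for the difference between 2 proportions will be calculated using the asymptotic Wald method". It mentions no stratum weights, stratified variance, continuity correction, or exact or score alternative.

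SAP 7.6.2.2 sends the ≥50% responder endpoint to the same method: "Similarly, this endpoint will be analyzed as for" Section 7.6.2.1. SAP 7.6.2.4 does the same for discontinuation due to lack of efficacy: "Similarly, this endpoint will be analyzed as described in for" Section 7.6.2.1.

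SAP 7.6.2.4 derives that last event in steps. Step 1 is "Condition on the eCRF item if the patient stopped study treatment with reason of Lack of Efficacy". The patient's ADPS must then have risen by at least 30% from Baseline at the end of treatment. All other mITT patients count as not having the event. SAP 3.2 lists the endpoint as "Proportion of patients discontinuing treatment due to lack of efficacy defined as increase in ADPS" of 30% from Baseline.

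SAP 7.6 declares the secondary endpoints exploratory and unadjusted for multiplicity.

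**The concern.** The Wald interval for a difference in proportions relies on a normal approximation and on a variance estimated from the observed proportions. Both fail when an arm has no events or only one or two. An arm with no events contributes zero to the estimated variance, and if both arms have none the interval shrinks to the single point 0. A study report would then print a 95% interval of (0, 0), which asserts certainty from an absence of data.

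The definition in SAP 7.6.2.4 makes that situation plausible, and the SAP does not say what to do if it arises. At stake is the reported precision of one secondary endpoint. In sparse data the interval would often be too short, and could exclude zero on the strength of very few patients.

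**Working it through.** **Sample size.** The SAP gives no precision figure or event rate for the proportion endpoints, so the only plan figure to reproduce is the arm size in SAP 2.3: 75/(1 − 0.20) = 93.75, rounded to 94 per arm and 3 × 94 = 282 in total. It reproduces. The re-estimation ceiling is 351/3 = 117 per arm.

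**Why events are likely to be few.** The ADPS scale stops at 10 (SAP 3.1), so a 30% rise requires 1.3 × baseline ≤ 10, that is, baseline ≤ 10/1.3 = 7.69. The severe stratum has a rounded run-in mean of 8 to 9 (SAP 7.2), so nearly all of it cannot have the event. (The stratum uses the 14-day mean and Baseline the second week, so a few exceptions are possible.) All-cause dropout is assumed to be 20%, or 0.20 × 94 = 18.8 patients per arm, and lack-of-efficacy stops with a 30% worsening are a subset of these. I therefore *assume* true rates of 0.5% to 8% per arm, or 0.47 to 7.5 expected patients.

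**Formulas.** With x₁, x₂ events, n per arm and pᵢ = xᵢ/n:
- Wald: (p₁ − p₂) ± 1.96 × √[p₁(1 − p₁)/n + p₂(1 − p₂)/n]
- Coverage: the sum of Bin(x₁; n, π₁) × Bin(x₂; n, π₂) over all (x₁, x₂) whose interval contains π₁ − π₂
- Chance of zero width through no events in either arm: [(1 − π₁)(1 − π₂)]ⁿ

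For example, at 1% in each arm: 0.99¹⁸⁸ = 0.151.

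**Exact results, n = 94 per arm.**

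| True rates | Wald coverage | Newcombe coverage | Chance of zero width |
|---|---|---|---|
| 0.5% vs 2% | 84.8% | 99.6% | 9.3% |
| 1% vs 2% | 90.0% | 99.3% | 5.8% |
| 1% vs 3% | 92.2% | 99.2% | 2.2% |
| 1% vs 5% | 93.6% | 97.2% | 0.3% |
| 2% vs 5% | 93.1% | 97.4% | 0.1% |
| 2% vs 8% | 93.7% | 96.5% | <0.1% |
| 1% vs 1% | 98.8% | 99.8% | 15.1% |
| 2% vs 2% | 96.2% | 98.6% | 2.2% |
| 3% vs 3% | 95.3% | 97.4% | 0.3% |
| 4% vs 4% | 95.0% | 96.7% | <0.1% |
| 5% vs 5% | 94.7% | 96.4% | <0.1% |

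Over a 0.5% to 8% grid in steps of 0.25 points, Wald is below 95% in 88% of all pairs and 90% of unequal pairs. Its mean is 93.7% and its minimum 69.1% (0.5% vs 0.75%). Newcombe is never below 95.6%, with mean 97.0%. At 117 per arm, Wald still covers only 90.0% at 0.5% vs 2% and 89.4% at 1% vs 2%.

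**Two concrete outcomes.**
- 0/94 vs 0/94: Wald gives (0, 0). The Wilson upper limit for 0/94 is 3.84/(94 + 3.84) = 0.039, so Newcombe gives (−3.9%, +3.9%).
- 0/94 vs 4/94: the difference is −4.26% and the standard error √(0.0426 × 0.9574/94) = 2.08%, so Wald gives (−8.3%, −0.2%), which excludes zero. Newcombe gives (−10.4%, +0.5%). Fisher's exact p is 0.12.

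**Responder endpoints.** At 30% vs 45%, Wald covers 94.6% and Newcombe 94.9%. In simulation with response rates 0 to 20 points apart between strata, the plain Wald interval is 0.5% to 2.4% wider than a stratified one. It disagrees with the CMH p-value at 0.05 in 0.2% to 1.7% of trials, rising to 5.7% for an extreme gap between strata (50% vs 15%).

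**The case against.** The defence is strong on several points.

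**Under-coverage is not universal.** A reader might infer that Wald always falls short for rare events. It does not: at equal rates up to about 4% it meets or exceeds 95%. With somewhat more events it is close to nominal even when rates differ: 94.2% at 3% vs 5%, 94.3% at 5% vs 8%, 95.0% at 3% vs 8%. The 84.8% figure needs an arm with 0.47 expected events. This stands. One qualification is that part of the equal-rate coverage comes from zero-width intervals landing on a true difference of zero: at 1% each they supply 15.1 of the 98.8 percentage points.

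**Rarity is an inference.** No event rate appears in the documents. This stands too, and the rates above are labelled as assumptions.

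**Test and interval do not target different quantities.** A reader might infer a mismatch of estimands from a stratified test beside an apparently unstratified interval. CMH is a test, not an estimator. Randomisation is 1:1:1 in permuted blocks stratified by severity (Protocol 6.6). If the compared arms have equal numbers in each stratum, the Mantel-Haenszel weight n₁ₖn₀ₖ/nₖ is proportional to stratum size and the weighted difference equals the crude one. Near balance they nearly coincide, and essentially only the variance differs. That the interval is unstratified is itself read from the SAP's silence.

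**The responder endpoints are barely affected.** The figures confirm this, so they are not part of the defect.

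**Little depends on these intervals.** The endpoints are exploratory, no stated decision rule uses the intervals, and counts are tabulated by arm, so a reader would see that both were zero. This limits the severity. It does not justify prespecifying a method that can return (0, 0).

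**Conclusion.** The point holds for the lack-of-efficacy discontinuation endpoint, at minor severity. As written, the SAP carries an asymptotic Wald interval to an endpoint whose definition makes few events likely, with no provision for sparse or empty cells.

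The zero-width result follows from the formula whenever neither compared arm has an event. How often that happens, and how far coverage falls, depends on true rates that the documents do not give. Under the assumed 0.5% to 8% range, under-coverage is the usual result for unequal rates and is serious only when an arm expects about one event or fewer. The documents do not support a claim of general under-coverage, of a mismatch in estimand, or of a material fault in the ≥30% and ≥50% responder analyses.

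**What to change.** In SAP 7.6.2.4, replace the cross-reference for the interval with its own sentence: a score-type 95% interval for the risk difference (Miettinen-Nurminen or Newcombe), stratified by baseline pain severity to match the CMH test. Add what will be reported when neither arm has an event, since the CMH statistic is then undefined as well. A stratified Wald interval would not be enough, because it still collapses at 0 versus 0.

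Using the same stratified interval for the two responder endpoints is optional, for consistency, and would change the numbers negligibly.

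The cost is one SAP sentence and a programming option, with no effect on data collection or the primary analysis. The downside is wider, somewhat conservative intervals for rare events: Newcombe covers about 96% to 99.9% at most of the rates examined.
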